7.1 Total Sample Size

Assuming we obtained the sensitivity (Se) of 0.92, specificity (Se) of 0.96, and disease prevalence (P) of 0.05 from the literature [9-11], we set the allowable error (d) to 0.08, with a confidence level of 95% (Z=1.96). When estimating the sample size using sensitivity, the formula yields

$$N = (1.962 * 0.95 * (1 - 0.95)) / 0.052 = 113$$

The sample size was estimated to be 113 cases according to theoretical calculation.

In addition, based on previous studies, the potential loss-to-follow-up rate for patients is estimated to be 5%-10%. This study anticipates a 10% loss-to-follow-up rate during the clinical trial, with a calculated total sample size of 120 cases. This is a multicenter study, with 80 cases from our center (The First Affiliated Hospital of Zhejiang University School of Medicine), 20 cases from Zhejiang Provincial People's Hospital, and 20 cases from Shulan Hangzhou Hospital.

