2.1 Content of Clinical Studies

2.1.1 Evaluation of the Diagnostic Performance of 18F-FAPI PET/CT

This study aims to evaluate the sensitivity, specificity, and accuracy of 18F-FAPI PET/CT in lung cancer patients, providing a basis for clinical application. By performing 18F-FAPI PET/CT scans on lung cancer patients and collecting relevant data, the performance of this modality in early diagnosis, staging, and recurrence monitoring was analyzed. The goal is to provide a scientific basis for clinical decision-making in the diagnosis and treatment of lung cancer.

2.1.2 Comparative Study of 18F-FAPI PET/CT with Other Imaging Techniques (CT, MR, FDG PET/CT)

A comparative study of 18F-FAPI PET/CT versus conventional imaging modalities (CT or MR) or 18F-FDG PET/CT in lung cancer patients, evaluating the differences in tumor detection sensitivity, specificity, and accuracy among various imaging techniques. The study aims to clarify their advantages in clinical applications for lung cancer. The research will focus on analyzing the differences in tumor size, location, metastasis, and pathological characteristics among the imaging techniques, exploring the potential of 18F-FAPI PET/CT in improving diagnostic accuracy and early detection of lung cancer.

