2.1.3 Diagnostic differences in the 18F-FAPI PET/CT analysis of lung cancer subgroups

Subgroup analysis was performed based on pathological type, stage, and molecular subtype, stratified by disease pathological type (adenocarcinoma/squamous cell carcinoma/small cell lung cancer), stage (early/advanced), and molecular subtype (EGFR mutation-positive, ALK-positive, ROS1-positive). The aim was to evaluate the differences in sensitivity and specificity of 18F-FAPI PET/CT across different patient populations. This study will help identify which specific types of lung cancer patients are more likely to benefit from 18F-FAPI PET/CT, thereby providing a basis for the development of individualized treatment plans.

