5.3.3 Subject Loss to Follow-up

Lost to follow-up: Participants did not complete the specified follow-up period but did not 'formally' withdraw from the clinical trial.

If a participant fails to respond to three telephone follow-ups, a registered mail letter must subsequently be sent to the participant. If the participant does not respond to the letter, the participant will be considered as having "lost to follow-up" for current study visits or telephone contacts. The investigator must record this information on the original data sheet. The investigator must report this information to the relevant ethics committee in accordance with the procedures of their institution.

For cases with lost-to-follow-up, the reasons should be explained, and their e-CRF forms should be retained for review. No diagnostic efficacy statistical analysis will be performed, but the patients who undergo examinations may participate in safety analysis as appropriate.

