5.4 Study Endpoints

Primary endpoint: Diagnostic efficacy of 18F-FAPI PET/CT in lung cancer patients (sensitivity, specificity, accuracy)

secondary end points:

- ① Compare the diagnostic performance differences of 18F-FAPI PET/CT with CT, MR, and 18F-FDG PET imaging in clinical applications for lung cancer;
- ② Analysis of diagnostic differences in the subgroup of patients (pathological, genetic, etc.) using 18F-FAPI PET/CT;
- ③ Evaluation of 18F-FAPI PET/CT in predicting lung cancer prognosis.

6 Research Procedures and Operational Standards

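### The planned sample size does not follow from its own inputs: the stated values give 45, the printed formula gives 73, and neither gives 113 or leads to 120

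*Protocol*

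**What the plan says.** Section 5.4 gives the primary endpoint as "Diagnostic efficacy of 18F-FAPI PET/CT in lung cancer patients (sensitivity, specificity, accuracy"), so three measures share primary status. Section 5.3.1 admits patients with suspected or confirmed lung cancer.

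Section 7.1 takes a sensitivity of 0.92 and a specificity of 0.96 from the literature, together with a "disease prevalence (P) of 0.05 from the literature [9-11], we set the allowable error (d) to 0.08". It sizes on sensitivity alone, with the words "When estimating the sample size using sensitivity, the formula yields", and prints "N = (1.962 * 0.95 * (1 - 0.95)) / 0.052 = 113". It continues: "This study anticipates a 10% loss-to-follow-up rate during the clinical trial, with a calculated total sample size of 120 cases". For patients lost to follow-up, section 5.3.3 says "No diagnostic efficacy statistical analysis will be performed".

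Section 2.1.3 plans subgroups by histology, stage and EGFR, ALK or ROS1 status, and says of them: "The aim was to evaluate the differences in sensitivity and specificity of 18F-FAPI PET/CT across different patient populations".

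**The concern.** A reader of section 7.1 should be able to put the stated inputs into the stated formula and obtain the stated number. Here the text and the formula use different values for both sensitivity and allowable error, and the printed result matches neither. The prevalence and the specificity are quoted but enter no formula.

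Two further steps look doubtful. A precision formula for sensitivity gives a number of reference-positive patients, but the result is treated as a total for a mixed cohort. The allowance for loss also does not take 113 to 120.

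At stake is what the trial can say about its primary measures. The precision of sensitivity is misdescribed. The precision of specificity is left to whatever share of enrolled patients turns out not to have cancer. In the subgroups of section 2.1.3, specificity may have no denominator.

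**Working it through.** **Inputs** (section 7.1 unless noted): Z = 1.96; text sensitivity 0.92, text d 0.08; formula sensitivity 0.95, formula d 0.05; specificity 0.96; P 0.05; loss 10%; N = 120; lost patients leave the efficacy analysis (section 5.3.3). The printed 1.962 and 0.052 are read as 1.96² and 0.05² with superscripts lost in extraction; this is not counted as an error.

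**1. Reproducing 113.** n = Z² p(1 − p)/d², with Z² = 3.8416.

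| p | d | Calculation | n | Where the pair is stated |
|---|---|---|---|---|
| 0.95 | 0.05 | 3.8416 × 0.0475 / 0.0025 | 72.99 → 73 | printed formula |
| 0.92 | 0.08 | 3.8416 × 0.0736 / 0.0064 | 44.18 → 45 | text |
| 0.92 | 0.05 | 3.8416 × 0.0736 / 0.0025 | 113.10 (114 rounded up) | nowhere |

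The likely source of 113 is the third pair, which takes its sensitivity from the text and its error from the formula.

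**2. What the number counts.** Sensitivity is estimated only in patients with cancer, so each n above is a count of cancer patients. Turning it into a total requires the cancer share of the cohort. The stated P = 0.05 cannot be that share in suspected or confirmed cases: 108 × 0.05 = 5.4 cancers.

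**3. Loss step.** 113/0.9 = 125.6, so 126 enrolled. Going from 113 to 120 covers a loss of 1 − 113/120 = 5.8%. With 10% loss, 120 × 0.9 = 108 evaluable.

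**4. Sensitivity at 108.** If all 108 had cancer, the half-width at 0.92 is 1.96 × √(0.0736/108) = 0.051, so d = 0.05 is not met at that sensitivity. On the printed pair (0.95, 0.05), 73 cancers are needed, which is 73/108 = 68% of the evaluable patients. On the text pair (0.92, 0.08), 45 are needed, or 45/108 = 42%. Both can fit within 108, depending on the cancer share.

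**5. Precision at assumed non-cancer shares.** The protocol gives no share, so these are assumptions. Intervals are exact (Clopper-Pearson) 95%, at the count nearest 0.96 for specificity and 0.92 for sensitivity.

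| Non-cancer share of 108 | Specificity | Interval | Sensitivity | Interval |
|---|---|---|---|---|
| 10% | 11/11 | 0.72-1.00 | 89/97 | 0.84-0.96 |
| 20% | 21/22 | 0.77-1.00 | 79/86 | 0.84-0.97 |
| 30% | 31/32 | 0.84-1.00 | 70/76 | 0.84-0.97 |

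Sensitivity hardly changes over this range. Specificity changes a good deal.

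**6. Normal formula against exact intervals.** With 45 cancers, 41/45 gives 0.788-0.975, a half-width of (0.975 − 0.788)/2 = 9.4 points. For specificity the normal formula at d = 0.08 gives 3.8416 × 0.0384/0.0064 = 23.05, so 24 negatives, but 23/24 gives 0.789-0.999, a half-width of 10.5 points. Counts that meet 8 points by the normal formula therefore miss it by exact intervals.

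**7. Subgroups.** Section 7.3 defines specificity as TN/(TN + FP). Every group in section 2.1.3 is defined by having lung cancer. If the target is lung cancer yes/no per patient, TN + FP = 0 in each group and specificity is 0/0. If the unit is a lesion or node, it can be computed.

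**The case against.** The fairest defence has four parts.

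- **The mismatch is a slip.** Entering 0.92 in the formula does restore 113. It does not remove the conflict with the stated d of 0.08, the failed loss step, or the use of a cancer count as a total. The quoted loss range of 5-10% would allow 120 at its lower end (113/0.95 = 118.9, so 119), but the section says that it plans for 10%.
- **Sizing on one measure is legitimate and openly declared.** This stands. Leaving specificity unsized is a design choice. A reader might infer that 120 is too small for specificity, but the documents do not support that: the non-cancer share is unknown, and precision could be adequate or poor. What is missing is a statement of the precision to expect.
- **The sponsor may have meant 0.95 with 0.05.** This also stands. A reader might infer that 120 can support only an error of 0.08. That is true only at sensitivity 0.92; the pair in the printed formula needs 73 cancers, which can fit within 108.
- **Target and unit may be settled in a statistical analysis plan that is not shown.** This stands in part. The image criteria in section 6.2 judge positivity in a lesion, and section 2.1.1 says "the performance of this modality in early diagnosis, staging, and recurrence monitoring was analyzed", which points to uses beyond a per-patient diagnosis. It would be too strong to say that subgroup specificity is impossible. The objective in section 2.1.3 has no denominator only on the per-patient cancer yes/no reading.

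**Conclusion.** The sample-size justification in section 7.1 is wrong as written. Its stated inputs give 45, its formula gives 73, and 113 needs a pair of values that appears nowhere together. At 10% loss 113 would need 126 enrolled, while 120 leaves about 108 evaluable patients of mixed disease status. This part is plain arithmetic and rests on no assumption beyond reading the lost superscripts as squares.

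The rest is narrower. Specificity, a primary measure, has no stated expected precision; its lower exact limit runs from about 0.72 to 0.84 over assumed non-cancer shares of 10-30%, and the true share is not given. A reader might also work out a range of cancer shares within which d = 0.08 holds for both measures. Such a range built on 45 cancers and 24 negatives should not be relied on, because those counts miss 8 points by exact intervals. The subgroup point is secondary and depends on the target and unit intended.

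None of this shows that 120 patients are too few or that the primary analysis cannot be run. The justification should be corrected before results are seen.

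**What to change.** Keep N = 120.

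1. **Section 7.1.**
   - Choose and justify one sensitivity and one allowable error, and use them in both text and formula. By the normal formula 0.92 with 0.08 needs 45 cancers and 0.95 with 0.05 needs 73, and either can fit within 108 depending on the cancer share; 0.92 with 0.05 needs 114 and cannot.
   - State that the result is a number of cancer patients.
   - Replace the prevalence of 0.05 with the expected cancer share of this cohort, or remove it.
   - Correct the loss step to 108 evaluable.
   - Present 120 as a fixed size. Give the expected precision of sensitivity and specificity over a plausible range of cancer shares, by one method (exact intervals), and do not claim that specificity is sized.
2. **Section 2.1.3 (secondary).** If the target is lung cancer yes/no per patient, compare sensitivity only in the histology, stage and molecular subgroups. Otherwise state that specificity there is per lesion or node, against pathology of the same site.

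The cost is protocol wording and one recalculation, with no added patients and no change to eligibility or the primary analysis set. The stated precision becomes less favourable, and subgroup specificity is lost unless site-level pathology is available.

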5.3 Subject Selection

5.3.1 Eligibility Criteria for Subjects

- (1) Patients with suspected or confirmed lung cancer
- (2) 18F-FAPI PET/CT has been performed.

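### Section 7.1: the stated inputs give 45, the printed formula gives 73, and the protocol reports 113; if 113 is the target, 120 does not cover the anticipated 10% loss

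*Protocol*

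**What the plan says.** Section 7.1 (Total Sample Size) bases the calculation on sensitivity. Its literature-based inputs are "sensitivity (Se) of 0.92", "specificity (Se) of 0.96" (the label should presumably be Sp) and a disease prevalence of 0.05. For precision it says "we set the allowable error (d) to 0.08, with a confidence level of 95% (Z=1.96".

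The next line gives the calculation: "N = (1.962 * 0.95 * (1 - 0.95)) / 0.052 = 113". A sentence below it confirms 113 as the theoretical sample size.

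On attrition, 7.1 says "the potential loss-to-follow-up rate for patients is estimated to be 5%-10" per cent, and continues: "This study anticipates a 10% loss-to-follow-up rate during the clinical trial, with a calculated total sample size of 120 cases". Section 5.3.3 (Subject Loss to Follow-up) says of lost cases: "No diagnostic efficacy statistical analysis will be performed".

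The eligible population in section 5.3.1 is "Patients with suspected or confirmed lung cancer". The protocol summary, section 5.1 and section 5.3.5 repeat the figure of 120 without further justification.

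**The concern.** The proportion and the allowable error change between the sentence that sets them (0.92 and 0.08) and the formula that uses them (0.95 and 0.05), and the printed result follows from neither pair. The step from 113 to 120 adds about 6%, although the text says 10% loss is expected.

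Sensitivity is part of the primary endpoint, and no hypothesis test or power is specified for it. The precision target is therefore the whole design criterion. If a reader cannot tell whether it is 5 or 8 percentage points, the reader cannot judge whether 120 patients are enough.

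**Working it through.** **Inputs.** From the text of 7.1: Se = 0.92, Sp = 0.96, P = 0.05, d = 0.08, Z = 1.96, loss 10% (range 5% to 10%), N = 113, total 120. From the printed formula: p = 0.95, d = 0.05. The formula is the usual precision formula for one proportion, n = Z² × p × (1 − p) / d².

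**Can 113 be reproduced?**

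| Inputs | Calculation | n |
|---|---|---|
| As printed in the formula | 1.96² × 0.95 × 0.05 / 0.05² | 72.99, so 73 |
| As stated in the text | 1.96² × 0.92 × 0.08 / 0.08² | 44.18, so 45 |
| Se from the text, d from the formula | 1.96² × 0.92 × 0.08 / 0.05² | 113.10 |

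Only the third row gives 113 from values that appear in 7.1 (strict rounding up would give 114). The pair p = 0.95 and d = 0.04 gives 114.05, but 0.04 is stated nowhere. Lost superscripts are not the cause: with 1.962 and 0.052 read as plain numbers, the expression equals about 1.8. Other variants of the stated inputs also fail: a one-sided Z gives about 31, a continuity correction about 56, and specificity in place of sensitivity 24.

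**Does 120 cover the loss?**

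- Needed for 113 after 10% loss: 113 / 0.9 = 125.6, so 126. The cruder 113 × 1.1 = 124.3 gives 125.
- Left from 120 after 10% loss: 120 × 0.9 = 108, which is below 113.
- Largest loss that 120 can absorb: 1 − 113/120 = 5.8%, near the low end of the protocol's range. At 5% loss, 120 × 0.95 = 114 remain.
- Had the other readings been meant, 120 would be ample: 73 / 0.9 = 81.1, so 82; 45 / 0.9 = 50.

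**What precision does 120 deliver?** Only patients with lung cancer contribute to sensitivity. The protocol gives no expected cancer share for this cohort, so the shares below are assumptions. Half-width = 1.96 × √(0.92 × 0.08 / n), with 108 evaluable:

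| Assumed cancer share | Cancer patients n | Half-width (points) |
|---|---|---|
| 100% (best case) | 108 | 5.1 |
| 90% | 97 | 5.4 |
| 80% | 86 | 5.7 |
| 50% | 54 | 7.2 |
| 42% | 45 | 7.9 |

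At 10% loss, ±5 points is missed for every cancer share. ±8 points is met if at least 45 of the 108 (45/108 = 42%) have cancer.

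**Prevalence.** P = 0.05 does not enter the printed formula. Applied to the stated inputs, it would require 44.18 / 0.05 = 884 patients in total. It also does not describe a cohort recruited because lung cancer is suspected or already confirmed.

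**The case against.** The strongest counter-argument is that little changes in practice. This is an estimation study with no power claim. If 113 was computed from Se = 0.92 and d = 0.05, the underlying calculation is sound and was merely misprinted. Falling from 113 to 108 evaluable then widens the half-width only from 5.0 to 5.1 points. That stands, and it is why the point is not that 120 is materially too small. However, the origin of 113 is an inference that the protocol does not state. Even if the 0.95 were a misprint for 0.92 in both places, d = 0.08 would still conflict with 0.05, and 120 with 126.

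A second objection is that keeping 120 prejudges the sponsor's choice of precision and looks at sensitivity alone, while the primary endpoint also includes specificity and accuracy. This stands in part. If ±5 points after 10% loss is a firm requirement, 120 falls short. On specificity, at Sp = 0.96 the assumed cancer shares of 90%, 80% and 50% leave about 11, 22 and 54 patients without cancer. The half-widths, 1.96 × √(0.96 × 0.04 / n), are then 11.6, 8.2 and 5.2 points. Section 7.1 sizes the study on sensitivity only, so this does not affect the error described here, but any statement that 120 is adequate must be limited to sensitivity.

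**Conclusion.** The concern holds. The sample-size paragraph is wrong as written: its inputs, formula and result give 45, 73 and 113, and neither text extraction nor any other section reconciles them. The loss allowance fails if 113 is the target, as 7.1 says it is: 108 evaluable remain at 10% loss, and 126 would have to be enrolled.

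The consequence for precision is modest if nearly all patients have cancer (5.1 points against 5.0) and grows as the share falls (7.2 points at an assumed 50%). These figures rest on Se = 0.92, the normal-approximation formula that the protocol itself uses, and 10% loss. The correction is needed because this is the trial's only size justification, and it leaves the precision target undetermined.

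**What to change.** Rewrite section 7.1 as follows:

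- Give one set of Se, d, formula and N that agree, and say that N counts patients with lung cancer. Correct the label on specificity.
- Delete P = 0.05, or replace it with the cancer proportion expected in this cohort.
- Keep 120 and state that 10% loss leaves 108 evaluable.
- State the half-width for sensitivity at Se = 0.92: about 5.1 points if all 108 have cancer, and about 5.4 to 7.2 points for assumed cancer shares of 90% to 50%. Do not claim ±5 points after 10% loss.
- If d = 0.08 is kept, say that it needs 45 lung-cancer patients and is met if at least 45 of the 108 have cancer.

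The half-width for specificity at the expected cancer share would be a useful addition.

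The cost is protocol wording, plus ethics re-approval if the change counts as more than administrative under section 6.1. No extra patients are needed, provided the sponsor accepts a stated precision slightly worse than the ±5 points that 113 implies. If the sponsor insists on ±5 points after 10% loss, 120 cannot support it.

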7.2 Significance Level and Power of Clinical Studies

The significance level α was set at 0.05; the confidence level was 0.95.

7.3 Statistical Methods

Statistical analysis was performed using SPSS 17.0. The diagnostic sensitivity, specificity, and negative/positive predictive values were calculated using a four-cell table. The area under the ROC curve and the optimal cutoff value (SUV optimal cutoff) were evaluated by ROC curve analysis. The consistency between 18F-FAPI PET/CT diagnosis and pathological diagnosis was assessed using the kappa test. A p-value <0.05 was defined as statistically significant.

Statistical analysis was performed using SPSS 17.0.

① Diagnostic performance evaluation, four-grid table index calculation:

Sensitivity = True positives / (True positives + False negatives) × 100%

Specificity = True Negative / (True Negative + False Positive) × 100%

Positive predictive value = true positive / (true positive + false positive)

Negative predictive value = true negative / (true negative + false negative)

② ROC curve analysis:

Calculate the area under the curve (AUC) and evaluate diagnostic performance (AUC>0.9 indicates excellent, 0.8-0.9 indicates good, 0.7-0.8 indicates moderate).

Determine the optimal cutoff for SUV using the maximum Youden index.

③ consistency check

The consistency between 18F-FAPI PET/CT and pathological diagnosis was evaluated using the Kappa coefficient.

Kappa>0.8: Excellent consistency;

0.6-0.8: High consistency;

<0.6: Consistency should be interpreted with caution.

Bilateral test, $p<0.05$ defined as significant difference.

④ survival analysis

Kaplan-Meier method:

Collect baseline PET parameters (lesion SUVmax, lesion SUVmean, MTV, LTV, bone marrow SUVmax, etc.), and plot PFS/OS curves according to treatment response (CR/PR vs. SD/PD), pathological response (e.g., MPR status), or PET parameter grouping (e.g., high/low SUVmax). Compare the significance of survival differences between groups using the Log-rank test ($p<0.05$).

Cox proportional hazards model:

Univariate analysis: Screening of clinical variables associated with PFS/OS (age, stage, SUVmax, MTV, etc.).

Multivariate analysis: Significant univariate variables ($p<0.1$) were included, with quantified hazard ratios (HR) and 95% confidence intervals.

Verify the proportional hazards assumption (Schoenfeld residual test).

8 Data Recording and Management

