5.2.2 Clinical Indicator Assessment

The gold standard is the pathological result of biopsy or surgery.

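### Confirmed and still-suspected patients are not separated in the four-cell analysis, so PPV, NPV and kappa depend on how many confirmed cases happen to be recruited

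*Protocol*

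**What the plan says.** Protocol section 5.3.1 opens the study to "Patients with suspected or confirmed lung cancer" who have had an 18F-FAPI PET/CT. It sets no quota or ratio for the two groups among the 120 planned subjects. Section 5.2.2 fixes the reference: "The gold standard is the pathological result of biopsy or surgery". Section 5.4 names sensitivity, specificity and accuracy as the primary endpoint; PPV, NPV and kappa are not named endpoints.

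On analysis, section 7.3 says "The diagnostic sensitivity, specificity, and negative/positive predictive values were calculated using a four-cell table". It prints one formula for each of these four measures, none for accuracy, and no restriction by diagnostic status. It assesses agreement between PET and pathology by kappa, and grades kappa above 0.8 as the top band, 0.6 to 0.8 as the next, and below 0.6 as needing caution. The subgroups in section 2.1.3 are pathological type, stage and molecular subtype; suspected versus confirmed is not among them.

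Section 5.2.1 says there is no blinding. The history-taking part of section 6.2 collects biopsy history and recent pathological results.

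**The concern.** A patient whose lung cancer is already proven is reference-positive on entry. For the patient-level diagnosis of lung cancer, that patient can fall only in the true-positive or false-negative cell. Every true negative and false positive must come from the suspected group. If both groups enter one table, each added confirmed patient raises the cohort prevalence. PPV then rises, NPV falls and kappa shifts, although the scan performs no differently.

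The reported NPV and kappa band would then partly describe recruitment at the three centres. A reader who takes the NPV as the chance that a suspected patient with a negative scan is free of cancer could be badly misled.

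Sensitivity is exposed by another route. Readers are not blinded and pathology results are part of the collected history, so a scan may be read in the knowledge that the patient has cancer. That could raise sensitivity in the confirmed group.

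**Working it through.** **No plan figure to reproduce.** The protocol prints no expected accuracy, PPV, NPV or kappa. The 113 in section 7.1 is a sample-size figure and plays no part here.

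**Inputs from the protocol.** N = 120; Se = 0.92 and Sp = 0.96 (section 7.1).

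**Inputs assumed, because the protocol gives none.** Cancer rate among suspected patients q = 0.60. Number confirmed: 0, 60 or 90 of 120. The unit of analysis is the patient.

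**Pooled prevalence P.**
- 0 confirmed: 0.60 × 120 = 72 cancers, P = 0.60, 48 without cancer.
- 60 confirmed: 60 + 0.60 × 60 = 96 cancers, P = 0.80, 24 without cancer.
- 90 confirmed: 90 + 0.60 × 30 = 108 cancers, P = 0.90, 12 without cancer.

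**Formulas.**
- PPV = Se·P / [Se·P + (1 − Sp)(1 − P)]
- NPV = Sp(1 − P) / [Sp(1 − P) + (1 − Se)P]
- Accuracy = Se·P + Sp(1 − P), the usual definition
- Kappa = (accuracy − e)/(1 − e), where e = P·T + (1 − P)(1 − T) and T = Se·P + (1 − Sp)(1 − P)

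**Results at Se 0.92, Sp 0.96.**

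| Confirmed | PPV | NPV | Accuracy | Kappa |
|---|---|---|---|---|
| 0 | 0.552/0.568 = 0.97 | 0.384/0.432 = 0.89 | 0.936 | (0.936 − 0.5136)/0.4864 = 0.868 |
| 60 | 0.736/0.744 = 0.99 | 0.192/0.256 = 0.75 | 0.928 | (0.928 − 0.6464)/0.3536 = 0.796 |
| 90 | 0.828/0.832 = 0.995 | 0.096/0.168 = 0.57 | 0.924 | (0.924 − 0.7656)/0.2344 = 0.676 |

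Kappa leaves the protocol's top band through case mix alone. With 60 confirmed it rounds to 0.80 but lies just below the cut.

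**Range over the assumed cancer rate** (confirmed share 0% / 50% / 75%, same Se and Sp).

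| q | NPV | Kappa | Accuracy |
|---|---|---|---|
| 0.30 | 0.966 / 0.866 / 0.718 | 0.877 / 0.858 / 0.777 | 0.948 / 0.934 / 0.927 |
| 0.50 | 0.923 / 0.800 / 0.632 | 0.880 / 0.825 / 0.720 | 0.940 / 0.930 / 0.925 |
| 0.70 | 0.837 / 0.679 / 0.493 | 0.845 / 0.752 / 0.613 | 0.932 / 0.926 / 0.923 |

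NPV falls substantially in every row, and kappa drops below 0.8 in every row by 75% confirmed. Accuracy moves by about two points at most.

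**When accuracy would move.** Accuracy always lies between Se and Sp, so it shifts materially only if they are far apart. With an assumed Sp of 0.60 and q = 0.60, it is 0.552 + 0.240 = 0.79, then 0.736 + 0.120 = 0.86, then 0.828 + 0.060 = 0.89.

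**What case mix does not touch.** In this algebra Se and Sp are held constant, so case mix alone leaves them unchanged. The possible inflation of sensitivity by unblinded reading cannot be sized from the protocol.

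**The case against.** The strongest reply is that the primary endpoint is largely unaffected. Sensitivity and specificity do not depend on prevalence, and accuracy moves by 1.2 points at the plan's own values. The large shifts fall on measures that are not named endpoints. This stands. A reader might infer that the primary accuracy result is determined by the number of confirmed cases; the plan's figures do not support that.

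A reader might also infer that a weakly specific scan could hide behind high accuracy and PPV. The documents do not bear that out, because specificity is itself a primary measure and would show the weakness, though imprecisely if few patients without cancer enrol.

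Second, the protocol does not state the unit of the table. Section 6.2 defines a positive finding per lesion and records metastatic lesions, and section 2.1.1 includes staging and recurrence monitoring. In a lesion-level, node-level or recurrence analysis, confirmed patients can supply true negatives and false positives. This also stands, and it limits the point to the patient-level diagnosis of lung cancer. It does not rescue PPV or NPV if the questions are mixed in one table.

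Third, pooling is read from the absence of any split, and a statistical analysis plan, not available here, might separate the groups. That is possible. But eligibility, formulas and subgroups are written in the protocol, and followed as written they do not separate them.

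Finally, section 7.1 assumes "disease prevalence (P) of 0.05", at which PPV would be 0.046/0.084 = 0.55. It is tempting to cite this gap as evidence against pooling. It is not: a suspected-only table with 60% cancer gives PPV 0.97, so the gap remains after separation.

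**Conclusion.** The point holds in a limited form. For the patient-level diagnosis of lung cancer, section 7.3 as written lets the unfixed mix of confirmed and suspected patients drive PPV, NPV and kappa. With 60% cancer among suspected patients and 0 to 90 of 120 confirmed, NPV falls from 0.89 to 0.57, PPV rises from 0.97 to 0.995, and kappa falls from 0.87 to 0.68, across the protocol's 0.8 line. The exact values rest on the assumed cancer rate and confirmed share; the fall in NPV holds throughout the range shown. Accuracy is little affected unless sensitivity and specificity differ widely. Sensitivity may be too high in confirmed patients because reading is unblinded, by an amount the protocol does not allow one to estimate.

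**What to change.** In section 7.3, for the patient-level diagnosis of lung cancer:

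- Compute PPV, NPV, kappa and accuracy in patients who had no malignant pathology at the time of the FAPI scan.
- Report sensitivity separately for suspected and confirmed patients, with the suspected-group value as the diagnostic result.
- Take status at scan from the biopsy and pathology history already collected under section 6.2, by comparing dates.
- Report the observed cancer rate in the suspected group beside PPV and NPV.
- Keep confirmed patients for separate lesion- or node-level staging and recurrence analyses, with the unit of each table stated.

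The work is analysis wording plus a derived status variable. Specificity loses nothing, since at patient level all its patients are in the suspected group already. The other measures lose precision. In the scenarios above, sensitivity would rest on 72, 36 or 18 suspected patients with cancer instead of 72, 96 or 108. By 1.96 × √(0.92 × 0.08/n), the approximate 95% half-width is 0.063, 0.089 or 0.125 instead of 0.063, 0.054 or 0.051. The suspected-only predictive values still apply only at the observed cancer rate: with none confirmed, NPV is 0.966 at a rate of 30% and 0.837 at 70%.
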